#### **9.4.3.1 Objective Response Rate and Clinical Benefit Rate**

ORR is defined as the proportion of subjects with a partial response, or better. Summaries of eg, VGPR and CBR will be provided with ORR as appropriate.

Disease-specific best overall response (BOR) will be summarized in conjunction with the ORR. The estimated rates and the exact 2-sided 95% confidence intervals (CI) (using the Clopper-Pearson method) will be summarized. Individual subject data listings will be provided.

The ORR for subjects treated with GEN3014, as compared to the ORR in subjects treated with daratumumab SC in the Expansion Part B with anti-CD38 mAb-naïve RRMM subjects, will be presented by the response ratio and the corresponding 2-sided 95% confidence interval based on the Miettinen-Nurminen method ([Newcombe, 1998](#)). P values will not be presented.

#### **9.4.3.2 Duration of Response**

DOR is defined as time from first response (PR or better) to timing of disease progression or death (due to any cause), whichever comes first. The analysis only applies to those with a response (PR or better).

Date of progression will be censored as planned for progression-free survival (PFS).

DOR distribution will be estimated using the Kaplan-Meier method, and the survival curve, median and 95% CI of the median will be presented. If there are too few responders, this analysis may be omitted. Individual subject data listings will be provided.

#### **9.4.3.3 Time-to-Response**

Time-to-response (TTR) is defined as the time from date of first dose, or date of randomization for subjects in the Expansion Part B, to time of response (PR or better). TTR will be summarized and presented descriptively for those with a response (PR or better).

#### **9.4.3.4 Progression-Free Survival**

PFS is defined as the time from the date of first dose, or date of randomization for subjects in the Expansion Part B, to the date of progression or death (due to any cause), whichever comes first. PFS will be censored similar to Table C1 in Appendix C in the FDA Guidance for Industry: Clinical Trial Endpoints for the Approval of Non-small Cell Lung Cancer Drugs and Biologics ([FDA Guidance, 2015](#)), with further details to be provided in the SAP.

The PFS distribution will be estimated using the Kaplan-Meier method, and the Kaplan-Meier curves, medians, and 95% CIs of the medians will be presented. The number of events may be small, and thereby limit use of the Kaplan Meier method to provide reliable information. In this case, descriptive statistics (eg, n, mean, standard deviation, median, minimum, and maximum) for PFS will be presented.

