## 9 STATISTICAL CONSIDERATIONS

The statistical analysis of the data collected in this trial is the responsibility of the sponsor. The objectives and endpoints for the 3 trial parts are tabulated in [Table 3-1](#) (Dose Escalation), [Table 3-2](#) (Expansion Part A [GEN3014 Single Cohorts]), and [Table 3-3](#) (Expansion Part B [Randomized H2H]). This section will (without particular reference to trial part) outline the planned analysis for each endpoint. The analyses will be detailed further in the Statistical Analysis Plan (SAP) to be finalized before database lock.

All presentations will be done separately for the different trial parts. Subjects in the Dose Escalation part will be analyzed according to the DL received. Subjects in Expansion Part A (GEN3014 Single Cohorts) will be analyzed according to their assigned expansion cohort. Subjects in Expansion Part B (Randomized H2H) will be analyzed according to their assigned treatment.

Statistical deliveries (tables, listings, and figures) may be produced for the following milestones:

- Periodic DMC reviews
- **Dose Escalation:** Primary safety and efficacy analyses will be conducted on all subject data at the end of the escalation, at latest 6 months after last patient first dose. Separate deliveries may be planned for the RRMM and R/R AML disease cohorts as feasible.
- **Expansion Part A (GEN3014 Single Cohorts)** consists of 4 parallel cohorts:
  - Anti-CD38 mAb-naive RRMM cohort
  - Anti-CD38 mAb-refractory RRMM cohort
  - R/R DLBCL cohort
  - R/R AML cohort

Each cohort will assess the disease-specific anti-tumor activity of GEN3014. No comparisons between cohorts are planned. Each cohort may report its individual primary analysis. The primary analyses will be conducted on all subject data, at latest 6 months after last patient first dose in respective expansion cohort. Timing of futility analyses in DLBCL cohort is described below.

- **Expansion Part B (Randomized H2H)** in anti-CD38 mAb-naive RRMM subjects: Primary safety and efficacy analyses will be conducted on all subject data, at latest 6 months after last patient first dose.
- The final analyses will be reported as an addendum to the primary analyses, based on the accumulated data up to 5 years after study start.

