#### **9.4.3.5 Overall Survival**

Overall survival (OS) is defined as the time from the date of first dose, or date of randomization for subjects in the Expansion Part B, to the date of death due to any cause. Subjects who withdrew consent to study or are lost to follow up will be censored at the latest date the subject was known to be alive (on or before the cutoff date).

The OS distribution will be estimated using the Kaplan-Meier method, and the Kaplan-Meier curves, medians, first and third quartiles and 95% CIs of the medians will be presented. The number of events may be small, and thereby limit use of the Kaplan Meier method to provide

reliable information. In this case, descriptive statistics (eg, n, mean, standard deviation, median, minimum and maximum) for OS will be presented.

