#### ***9.4.3.6 Time to Next Therapy***

Time to next therapy (TTNT) for subjects in the Expansion Part B is defined as the time from randomization to the start of subsequent anti-cancer therapy. Death due to PD without start of subsequent therapy will be considered as an event. Subjects who withdrew consent to study or are lost to follow up or die due to causes other than disease progression will be censored at their last disease assessment.

TTNT will be summarized similarly to OS.

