## 6 SUPPORTING DOCUMENTATION

### 6.1 Appendix 1: Changes to Protocol-planned Analyses

Not applicable.

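### When events are few, the protocol falls back on plain descriptive statistics of PFS, OS and TTNT that ignore censoring; the SAP omits this fallback but does not withdraw it

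*Protocol*

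**What the plan says.** Protocol 9.4.3.4 starts from the standard method: "The PFS distribution will be estimated using the Kaplan-Meier method, and the Kaplan-Meier curves, medians, and 95% CIs of the medians will be presented". It then continues: "The number of events may be small, and thereby limit use of the Kaplan Meier method to provide reliable information". The next sentence gives the consequence: "In this case, descriptive statistics (eg, n, mean, standard deviation, median, minimum, and maximum) for PFS will be presented". Protocol 9.4.3.5 repeats this for OS: "In this case, descriptive statistics (eg, n, mean, standard deviation, median, minimum and maximum) for OS will be presented". For TTNT, 9.4.3.6 says only: "TTNT will be summarized similarly to OS".

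The protocol does not say how many events count as small, or how a censored time enters the mean, SD or median. The times are certainly censored. For OS, for example, 9.4.3.5 censors anyone lost to follow-up or withdrawing consent at the last date of known survival.

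The SAP differs. Section 5.1 sets Kaplan-Meier for time-to-event variables in general, with the number and percentage of events and censorings. Sections 5.4.5 to 5.4.7 apply it to PFS, OS and TTNT, with rates at 6, 9 and 12 months for PFS and OS. None of these sections contains a few-events fallback. SAP Appendix 1, on changes to protocol-planned analyses, reads "Not applicable". The SAP states that it is based on protocol version 5.0 (Amendment 3); the current protocol is version 8.0 (Amendment 5).

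**The concern.** PFS, OS and TTNT are times to an event. If few subjects have had the event, most recorded times say only that the subject was event-free up to then. A plain mean or median can be formed in two ways, and neither estimates the endpoint:

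- Over all subjects, each censoring time is treated as if it were an event time. The result follows how long subjects have been observed.
- Over subjects with events only, just the earliest failures remain. The result is biased short.

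The rule therefore applies when censoring is heaviest. It also prints a finite median where the Kaplan-Meier median would properly be reported as not reached.

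The protocol is more careful elsewhere. With too few responders, the DOR analysis may be omitted and individual data are listed (9.4.3.2). Plain statistics for TTR are harmless because TTR is summarised only in subjects who responded (9.4.3.3).

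At stake are the PFS, OS and TTNT summaries at an early data cutoff. A programmer who followed the protocol and one who followed the SAP would produce different tables from the same data.

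**Working it through.** **No figure to reproduce.** The documents give no planning median, event count or power for PFS, OS or TTNT. The survival medians and accrual periods below are assumptions, except the 8-month OS median that Protocol 2.1.1.1 cites for myeloma refractory to a PI and an IMiD. For Part B the timing is: "Primary safety and efficacy analyses will be conducted on all subject data, at latest 6 months after last patient first dose".

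**Small example.** Take ten subjects, with events at 2 and 5 months and censoring at 6, 6, 7, 7, 8, 8, 9 and 9 months. The plain mean is 67/10 = 6.7, the SD 2.1 and the plain median 7.0 months. The Kaplan-Meier median is not reached, and the 6-month event-free rate is 8/10 = 0.80. The 7.0 is a follow-up time.

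**Closed form.** Let T be exponential with true median m, and C uniform on (a, b) by administrative censoring. For t between a and b:

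- P(min(T, C) > t) = 2^(−t/m) × (b − t)/(b − a). The plain median is the t that makes this 0.5.
- Event share = 1 − [m / ((b − a) ln 2)] × (2^(−a/m) − 2^(−b/m)).

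Follow-up of 3 to 9 months corresponds, for example, to a cutoff 3 months after the last first dose with 6 months of accrual:

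- m = 12: at t = 5.0, 0.749 × 4/6 = 0.50, so the plain median is 5.0. Event share = 1 − 2.885 × (0.841 − 0.595) = 0.29. The plain median is (12 − 5.0)/12 = 58% too low. The events-only median, by simulation, is 2.7.
- m = 24: at t = 5.48, 0.854 × 3.52/6 = 0.50, so the plain median is 5.5. Event share = 1 − 5.771 × (0.917 − 0.771) = 0.16.

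A true gap of 12 months shows as 0.5 months.

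**Cutoff at the 6-month limit.** Simulation with n = 40, 6 months of uniform accrual and 4,000 runs per row; median potential follow-up is 9.0 months:

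| True median | Events | Plain mean | Plain median | Events-only median | KM median not reached | KM 6-month rate (true) |
|---|---|---|---|---|---|---|
| 8 | 54% | 6.2 | 6.6 | 3.6 | 11% | 0.59 (0.59) |
| 24 | 23% | 7.9 | 8.2 | 4.2 | 96% | 0.84 (0.84) |
| 48 | 12% | 8.4 | 8.6 | 4.4 | 99% | 0.92 (0.92) |

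Doubling true survival from 24 to 48 months moves the plain median by 0.4 months. Plain means and medians at n = 10 and n = 20 are within 0.2 months of these. The 6-month rate agrees with truth here partly because nobody is censored before 6 months in this setting.

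**Moving only the cutoff.** With the true median fixed at 24 months and 6 months of accrual, cutoffs at 6, 12 and 24 months after the last first dose give plain medians of 8.2, 13.6 and 24.0. Survival is unchanged; only the calendar has moved. The match at 24.0 is coincidental.

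**How plausible is the trigger?** Protocol 4.4.1 estimates 4 months of treatment for RRMM and DLBCL and 3 months for AML, with treatment running until progression, toxicity or withdrawal. That is not a PFS assumption. If 4 months is nevertheless taken as an exponential PFS median, follow-up of 3 to 9 months gives an event share of 1 − 0.962 × (0.595 − 0.210) = 0.63, and follow-up of 6 to 18 months gives 0.85. Neither is a few-events case. For OS the protocol estimates about 17 months of post-treatment follow-up per RRMM subject, so many deaths could fall after the primary cutoff. With the cited 8-month OS median, however, 54% would already have died.

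**The case against.** The strongest objection is that the SAP already does it properly. Protocol section 9 leaves analysis detail to the SAP, and the SAP plans Kaplan-Meier, event and censoring counts, and landmark rates. If the SAP governs, little goes wrong in practice. This stands, and it lowers the risk. It does not remove the problem, because the SAP never says that the protocol rule is dropped.

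Three stronger readings are tempting, and the documents do not support them.

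- A reader might infer from "Not applicable" in SAP Appendix 1 that the protocol fallback governs. That entry was written against protocol version 5.0, which is not among the documents reviewed, so it cannot show that a rule in version 8.0 overrides the SAP. What can be said is that the two are unreconciled.
- A reader might infer that the fallback is likely to be used for PFS. With PFS near the protocol's treatment estimate, most subjects would have had an event by the primary cutoff. Small cohorts yield few events in number, but not necessarily mostly censored times, and the bias depends on the share censored.
- A reader might infer that a real difference between the Part B arms would be concealed. No test or hazard ratio is planned for these endpoints, no hypotheses are pre-defined (Protocol 9.1), and the primary endpoint is ORR. A final analysis on data up to 5 years after study start follows in any case.

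On wording, the protocol does not literally say that Kaplan-Meier is dropped. Replacement is the likelier reading, because the descriptive statistics follow a statement that Kaplan-Meier may be unreliable. Even if both were shown, the plain statistics would still mislead.

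**Conclusion.** The rule is wrong as written. For heavily censored times, a plain mean or median of PFS, OS or TTNT describes follow-up or early failures, not survival. Under exponential times and 3 to 9 months of follow-up, true medians of 24 and 12 months appear as 5.5 and 5.0. At a cutoff 6 months after the last first dose, with 6 months of accrual, true medians of 24 and 48 months appear as 8.2 and 8.6. These sizes rest on assumed medians, accrual periods and purely administrative censoring; the documents supply none of these for the endpoints concerned.

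The practical reach is limited. The endpoints are secondary and untested, so alpha, power, sample size and the primary endpoint are unaffected, and the SAP already plans the sound method. The exposure is greatest for OS at the primary cutoff, is not shown to be likely for PFS, and depends on which document the programming team follows. The point is worth correcting because the correction is specific and cheap.

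**What to change.** Add one line to SAP Appendix 1 stating that the few-events fallback in Protocol 9.4.3.4 and 9.4.3.5, and in 9.4.3.6 by reference, is not used for PFS, OS or TTNT. Delete the sentences at the next protocol amendment; they do not justify an amendment of their own.

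When events are few, present the SAP's Kaplan-Meier output with:

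- numbers at risk under the curve;
- number and percentage of events and of censorings;
- landmark rates only where enough subjects remain at risk;
- the median as *not reached* where that applies;
- individual times in a listing with a censoring flag, and no mean or SD of PFS, OS or TTNT.

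Median follow-up by reverse Kaplan-Meier would be a useful addition. Most of this is already in SAP 5.1 and 5.4.5 to 5.4.7. The cost is the SAP line and minor table programming, with no new data and no extra subjects. The protocol deletion needs a formal amendment under Protocol 10.1.4, which is why it should wait for the next one.

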#### **9.4.3.5 Overall Survival**

Overall survival (OS) is defined as the time from the date of first dose, or date of randomization for subjects in the Expansion Part B, to the date of death due to any cause. Subjects who withdrew consent to study or are lost to follow up will be censored at the latest date the subject was known to be alive (on or before the cutoff date).

The OS distribution will be estimated using the Kaplan-Meier method, and the Kaplan-Meier curves, medians, first and third quartiles and 95% CIs of the medians will be presented. The number of events may be small, and thereby limit use of the Kaplan Meier method to provide

reliable information. In this case, descriptive statistics (eg, n, mean, standard deviation, median, minimum and maximum) for OS will be presented.

#### ***9.4.3.6 Time to Next Therapy***

Time to next therapy (TTNT) for subjects in the Expansion Part B is defined as the time from randomization to the start of subsequent anti-cancer therapy. Death due to PD without start of subsequent therapy will be considered as an event. Subjects who withdrew consent to study or are lost to follow up or die due to causes other than disease progression will be censored at their last disease assessment.

TTNT will be summarized similarly to OS.

### **9.4.4 Exploratory Analysis**

#### ***9.4.4.1 Rate and Duration of MRD-Negative Remission***

The rate of MRD-negative remission is defined as the proportion of subjects with at least 1 MRD-negative sample. MRD-negative remission applies to RRMM in both the Dose Escalation and the Expansion, but only applies to R/R AML and R/R DLBCL in the Expansion.

Duration of MRD-negative remission is defined as the number of days from the date of the first documented MRD-negative sample to the date of MRD status change (not MRD-negative). This will be censored and analyzed using the same statistical methodology as for PFS.

### **9.4.5 Safety Analyses**

#### ***9.4.5.1 Adverse Events***

Summary tables for AEs will include only AEs that started, or pre-existing AEs that worsened, during the on-treatment period, ie, TEAEs.

The incidence of TEAEs (new or worsening from baseline) will be summarized by system organ class and/or preferred term; intensity based on grades of NCI-CTCAE v5.0 for all AEs (except for clinical TLS which is graded by the Cairo-Bishop classification); type of AE; and relationship to trial treatment.

Treatment-emergent SAEs will be tabulated.

All deaths (on-treatment and post-treatment) will be summarized.

All AEs, deaths, and SAEs (including those from the pre- and post-treatment periods) will be listed and those collected during the pretreatment and post-treatment period will be flagged.

Further summaries of AEs will be specified in the SAP.

#### ***Adverse Events of Special Interest***

Adverse events of special interest constitute the IRRs. These will be summarized as part of the other TEAEs. Symptoms of IRRs as collected in the eCRF may be provided in listings.

#### ***9.4.5.2 Clinical Laboratory Tests***

Grading of laboratory values will be assigned programmatically as per NCI-CTCAE v5.0. The calculation of CTCAE grades will be based on the observed laboratory values only, clinical assessments will not be taken into account.

CTCAE grade 0 will be assigned for all non-missing values not graded as 1 or higher.

For laboratory tests where grades are not defined by the CTCAE, results will be categorized as low/normal/high based on laboratory normal ranges.

The following summaries will be generated separately for hematology, and biochemistry tests:

- Listing of all laboratory data with values flagged to show the corresponding CTCAE grades, if applicable, and the classifications relative to the laboratory normal ranges.

For laboratory tests where grades are defined by the CTCAE:

- Worst post-baseline CTCAE grade (regardless of the baseline status). Each subject will be counted only once for the worst grade observed post-baseline.
- Shift tables using CTCAE grades to compare baseline to the worst on-treatment grade.

For laboratory tests where grades are not defined by the CTCAE:

- Shift tables using the low/normal/high/(low and high) (or other project-specific) classification to compare baseline to the worst on-treatment value.

#### **9.4.5.3 Vital Signs**

Data on vital signs will be tabulated and listed; notable values will be flagged.

#### **9.4.5.4 ECG Parameters**

Triplicates of 12-lead ECGs including PR, QRS, QT, heart-rate-corrected QT intervals using Fridericia's correction (QTcF), and RR intervals will be obtained for each subject. ECG data will be read and interpreted centrally.

Categorical analysis of QT/QTc interval data based on the number of subjects meeting or exceeding predefined limits in terms of absolute QT/QTc intervals or changes from baseline will be presented. In addition, a listing of these subjects will be produced (by cohort).

#### **9.4.6 Pharmacokinetic Analyses**

The PAS1 will be used for the analyses presented in this section.

Individual curves of concentration of trial drug vs time, including information on actual dose, will be presented for all subjects. All available data will be shown in these figures. The following PK parameters may be calculated based on the availability of data using non-compartmental methods:

- Maximum (peak) observed serum drug concentration ( $C_{\max}$ );
- Time to reach maximum (peak) serum drug concentration ( $t_{\max}$ );
- Area under the concentration-time curve (AUC) from time zero to last quantifiable sample ( $AUC_{\text{last}}$ ) and from time zero to 168 h ( $AUC_{0-168\text{h}}$ );
- Predose concentrations ( $C_{\text{trough}}$ ); and
- Subject-wise accumulation ratios in  $C_{\max}$  ( $R_{A,C_{\max}}$ ), AUC ( $R_{A,AUC}$ ) and  $C_{\text{trough}}$  ( $R_{A,C_{\text{trough}}}$ ) between Cycle 1 and Cycle 2 and in  $C_{\text{trough}}$  between Cycle 1 Day 8 and Cycle 3 Day 1.

Descriptive statistics of PK endpoints will include arithmetic and geometric means and standard deviations, CV%, median, minimum and maximum.

If deemed applicable, compartmental (population) PK modeling approaches will be applied. The results of the compartmental modeling will be documented outside the scope of the Clinical Study Report (CSR).

#### **9.4.6.1 Cycle 3 Day 1 Trough Concentration**

The PAS2 will be used for the analyses presented in this section.

The  $C_{trough}$  on Cycle 3 Day 1 is defined as a secondary endpoint in Expansion Part B, as part of the comparison of the 2 anti-CD38 mAb molecules. The  $C_{trough}$  levels in the 2 arms will be compared by calculating the geometric mean ratio and the corresponding 90% CI.

#### **9.4.7 Pharmacodynamic Analyses**

Pharmacodynamic analyses are designed to identify DLs at which GEN3014 is biologically active and to confirm the expected MOA of the drug (based on nonclinical studies) in human subjects. In the anti-CD38 mAb-naïve RRMM Expansion Part B, similar analyses may be performed on subjects treated with daratumumab SC in order to compare these with GEN3014 IV observations and identify differences and/or similarities in pharmacodynamic activity of both compounds.

Pharmacodynamic studies will include immunophenotyping analyses of the frequencies of NK cells and other leukocyte subsets as well as cytokine and complement analyses in peripheral blood. Curves of concentration of a pharmacodynamic marker vs time will be presented.

#### **9.4.8 Biomarker Analyses**

The BAS will be used for the analyses presented in this section.

The biomarker studies are designed to identify markers predictive of response (or resistance) to GEN3014. Correlation of baseline expression levels, or on-treatment changes in expression levels, with response, may identify responsive (or resistant) subgroups in addition to genes and pathways of which activity is altered following treatment with GEN3014. In the anti-CD38 mAb-naïve RRMM Expansion Part B, biomarker observations of subjects treated with GEN3014 IV may be compared to those of daratumumab SC-treated subjects in order to understand differences and/or similarities between both mAbs.

Any biomarker measures will be listed, tabulated, and where appropriate, plotted. Subjects will be grouped by prescribed dose.

Results of biomarker and pharmacodynamic analyses may be presented in a separate report. Planned analyses are conditional on the availability of clinically validated assays and may be deferred if emerging trial data show no likelihood of providing useful scientific information.

